# Trevo® Retriever Registry (China)

## Protocol Synopsis

Study Objective	
Primary Objective	To assess real world performance of the Trevo® Retriever which is intended to restore blood flow in the neurovasculature by removing thrombus in subjects experiencing ischemic stroke
Primary Endpoint	Revascularization status assessment at the end of the procedure using the modified TICI score
Secondary Endpoints	
 
1. Day 90 mRS assessment
 
2. Day 90 all-cause mortality
 
3. Neurological deterioration at 24 hours post procedure, defined as a four or more point increase in the NIHSS score from the baseline score
 
4. Rates of device and procedure related serious adverse events (AEs)
 

Other Key Assessments (Data points)	
 
1. Time points will be collected on and not limited to the following: stroke symptom onset, admission to hospital/emergency department, start of Intravenous tissue Plasminogen Activator (IV tPA), angio suite arrival, arterial puncture, clot integration, Trevo removal and end of procedure (defined as the time of the final cerebral angiogram)
 
2. Data on the use of accessory products in conjunction with Trevo
 
3. Costs of hospitalization, discharge disposition
 
4. Analysis of imaging (pre, angio, post) by an independent core lab
 
5. Compare Day 90 outcome with pre-stroke mRS, baseline imaging and symptom onset to time of treatment.
 

Registry Device	Any approved Trevo Retriever approved for use by the local regulatory agency
Control	N/A
Device Sizes	All Trevo product sizes approved for use by the local regulatory agency
Study Design	
Study Design	Prospective, open-label, multi-center, China local registry
Planned Number of Subjects	200 subjects
Planned Number of Sites / Countries	Up to 15 sites
Primary Efficacy Parameter	Post-procedural Modified TICI score
Follow-Up Schedule	
 
a. Day 30 telephone contact
 
b. Day 90 clinic visit
 

Key Inclusion Criteria	
 
1. Age <math>\geq 18</math>
 
2. Subjects experiencing acute ischemic stroke due to a large vessel occlusion who are eligible and suitable for restoration of blood flow using any approved Trevo Retriever in the neurovasculature to remove thrombus
 
3. Trevo Retriever is planned to be the primary mechanical neuro-thrombectomy device to remove the thrombus
 

**STRYKER CONFIDENTIAL** - THIS DOCUMENT CONTAINS CONFIDENTIAL AND PROPRIETARY INFORMATION THAT IS THE PROPERTY OF STRYKER CORPORATION. NEITHER THIS DOCUMENT NOR THE INFORMATION HEREIN MAY BE REPRODUCED, USED, OR DISCLOSED TO ANY THIRD PARTY WITHOUT THE PRIOR WRITTEN CONSENT OF STRYKER CORPORATION.

## Trevo® Retriever Registry (China)

Key Exclusion Criteria	4. Subject or subject's legally authorized Representative (LAR) has signed the study Informed Consent Form 5. Subject willing to comply with the protocol follow-up requirements
Key Exclusion Criteria	1. mRS >2 2. Any known coagulopathy 3. Anticipated life expectancy less than 3 months 4. Known absolute contraindications to the use of required study medications or agents (e.g., heparin, aspirin, clopidogrel, radiographic contrast agents, etc.) 5. Preexisting neurological or psychiatric disease that would prevent complete the study required evaluations 6. The subject is participating in another mechanical neuro-thrombectomy device trial or any other clinical trial where the study procedure or treatment might confound the study end point.
Statistical Methods	
Statistical Test Method	
There will be no sample size/or power estimation for this single-arm registry.
 
Data analysis will be performed under guidance from the Study PIs, Steering Committee, and Sponsor.

**STRYKER CONFIDENTIAL** - THIS DOCUMENT CONTAINS CONFIDENTIAL AND PROPRIETARY INFORMATION THAT IS THE PROPERTY OF STRYKER CORPORATION. NEITHER THIS DOCUMENT NOR THE INFORMATION HEREIN MAY BE REPRODUCED, USED, OR DISCLOSED TO ANY THIRD PARTY WITHOUT THE PRIOR WRITTEN CONSENT OF STRYKER CORPORATION.

## Trevo® Retriever Registry (China)

### 1 Introduction and Rationale

Stroke is the fifth most common cause of death and the leading cause of adult disability in the United States. Each year stroke afflicts approximately 795,000 Americans causing over 130,000 deaths. Stroke costs the nation \$34 billion annually which includes the cost of medical care, medications and loss of productivity. Around the world approximately 15 million people each year will endure a stroke resulting in an estimated 5.5 million deaths. Of those patients who are alive at 90 days after their stroke, 50% have some type of disability with 26% dependent on others for daily living and 20% require institutional care. One in six people worldwide will experience a stroke in their lifetime. Good clinical outcomes in ischemic stroke have been shown to be strongly linked to revascularization.

Intravenous tissue plasminogen activator (IV tPA) is the only FDA approved therapy for acute ischemic stroke and must be given within three (3) hours of ischemic stroke symptom onset. Unfortunately, only a small percentage of stroke patients receive IV tPA therapy, with estimates ranging from 2.4% to 9%. Even so, the effect of IV tPA in patients in acute ischemic stroke has a short therapeutic time window and is limited by the large thrombus burden that occurs in the setting of proximal arterial occlusion. One study reported that IV tPA has nearly no potential to recanalize occluded vessels with a thrombus length exceeding 8 mm. When administered, IV tPA achieves early recanalization in only 30%–50% of subjects, with even lower recanalization rates in proximal large vessel occlusions (middle cerebral, basilar artery, and carotid terminus). Subjects who are ineligible for IV t-PA or who fail IV t-PA therapy are candidates for treatment with the Trevo Retriever. The Trevo Retriever received CE mark on December 18, 2009 and was cleared by the FDA on August 13, 2012 to restore blood flow in the neurovasculature by removing thrombus in patients experiencing ischemic stroke within 8 hours of symptom onset. The Trevo Retriever also received FDA clearance on September 2, 2016 to restore blood flow in the neurovasculature by removing thrombus for the treatment of acute ischemic stroke to reduce disability in patients with a persistent, proximal anterior circulation, large vessel occlusion, and smaller core infarcts who have first received intravenous tissue plasminogen activator (IV t-PA). Patients should start treatment with the device within 6 hours of symptom onset.

### 2 Clinical Development Program for Trevo Retriever

The principal goal in treating acute ischemic stroke is to restore cerebral blood flow as rapidly and safely as possible. Two clinical trials, the Thrombectomy Revascularization of large Vessel Occlusions (TREVO) in acute ischemic stroke and the TREVO 2 study, were conducted using the Trevo Retriever. Both clinical studies demonstrated that mechanical neurovascular thrombectomy can safely and effectively be performed up to eight (8) hours after onset of acute ischemic stroke symptoms.

#### 2.1 TREVO Study

The TREVO study was a post marketing prospective, multi-center, single arm study performed at seven sites in Europe designed to quantify the performance of the Trevo Retriever in providing revascularization and clinical benefit to subjects experiencing a large vessel occlusion within 8 hours of symptom onset. The devices used in the study were the Trevo 4 x 20 mm, Trevo Pro 4, and Trevo 3 x 10 mm.

Sixty (60) subjects were enrolled between February 2010 and August 2011. Revascularization and intracranial hemorrhage at 24 hours were independently assessed by a central core lab. A Clinical

**STRYKER CONFIDENTIAL - THIS DOCUMENT CONTAINS CONFIDENTIAL AND PROPRIETARY INFORMATION THAT IS THE PROPERTY OF STRYKER CORPORATION. NEITHER THIS DOCUMENT NOR THE INFORMATION HEREIN MAY BE REPRODUCED, USED, OR DISCLOSED TO ANY THIRD PARTY WITHOUT THE PRIOR WRITTEN CONSENT OF STRYKER CORPORATION.**

## Trevo® Retriever Registry (China)

Events Committee (CEC) independently reviewed all protocol-defined safety endpoints to determine relationship to the device and the procedure, and the causes of all deaths.

The primary endpoint in TREVO was defined as angiographic revascularization as measured by the independent core lab using the TICI scale. Success was defined as a final TICI score of 2a or better. Post procedure, successful revascularization was achieved in 91.7% of subjects. In the TREVO study, operators were not restricted from using intra-arterial (IA) lytic, but it was only used in 10% of cases.

The secondary endpoints in TREVO were 90-day good clinical outcomes (defined as mRS of 0-2), 90 day mortality, device-related serious adverse events (DRSAEs) and symptomatic intracranial hemorrhage (SICH) at 24 hours (see **Table 1**).

Coincidentally, the rate of DRSAEs and SICH endpoints were both 5% (3/60), however the rates are not cumulative. One of the three SICHs was a DRSAE, while the other two were procedure-related. As mentioned above, one of the DRSAEs resulted in SICH while the other two DRSAEs were associated with subarachnoid hemorrhage (SAH).

**Table 1. TREVO Study Primary and Secondary Endpoints** 

Primary Effectiveness Endpoint	TREVO (N=60 subjects)
Revascularization	91.7% (55/60)
Secondary Endpoints	
90-Day Good Outcome (mRS = 0-2)	55.0% (33/60)
90-Day Mortality	20.0% (12/60)
Device-Related SAEs (DRSAEs)	5.0% (3/60)
SICH at 24 Hours (SITS-MOST)	5.0% (3/60)
SICH (ECASS III definition)	8.3% (5/60)

The TREVO protocol pre-defined specific events that were captured to assess safety which included vessel dissection, vessel perforations, ICH (as identified by core lab) and all deaths. Information for each of these events was collected and then independently adjudicated by the CEC. The results of this review are presented in **Table 2**. Most of the SAEs were attributed to the 12 deaths that occurred in the study, but a minority of the SAEs were related to the procedure (8.3%, 5 cases) or Trevo Retriever (5%, 3 cases).

**Table 2. TREVO Adjudicated Safety Events** 

Event	TREVO (N=60 subjects)
Serious Adverse Events (SAEs)	21.7% (13/60)
Procedure-Related SAEs	8.3% (5/60)
Device-Related SAEs	5.0% (3/60)

## Trevo® Retriever Registry (China)

### 2.2 TREVO 2 Study

The TREVO 2 study was an IDE trial designed to support a 510k application for FDA clearance in the U.S. The trial enrolled 178 subjects between February 3, 2011 and December 1, 2011 at 26 sites in the United States and one site in Spain. The subjects were randomized 1:1 to Trevo (N=88) or Merci (N=90) and were stratified by age and baseline NIHSS to ensure balance in the two arms. The devices used in the study were the Trevo 4 x 20 mm in 10 subjects, and the Trevo Pro 4 in 78 subjects. The subjects treated with Merci® Retrievers were treated with commercially available product, at the discretion of the treating physician.

The results for the primary effectiveness and safety endpoints are shown in the **Table 3**, and the results of the secondary endpoints are shown in **Table 4**.

**Table 3. Primary Endpoint Results per the TREVO 2 (ITT population)**

Endpoint	Trevo (N=88)	Merci (N=90)	Difference [95% CI] a	p-value
Primary Effectiveness Endpoint:				
Post-Device Revascularization Success (TICI 2a+)*	86.4% (76/88)	60.0% (54/90)	26.4% [13.2%, 39.0%]	< 0.0001 b < 0.0001 c
Primary Safety Endpoint:				
Composite Events ***	14.8% (13/88)	23.3% (21/90)	-8.6% [-20.7%, 3.2%]	0.1826 d
Vessel Perforation	1.1% (1/88)	10.0% (9/90)	-8.9% [-17.0%, -2.2%]	
Intramural Arterial Dissection	0.0% (0/88)	1.1% (1/90)	-1.1% [-6.1%, 3.1%]	
Symptomatic ICH	6.8% (6/88)	8.9% (8/90)	-2.1% [-10.7%, 6.4%]	
Embolization to Previously Uninvolved Territory	6.8% (6/88)	4.4% (4/90)	2.4% [-5.0%, 10.3%]	
Access Site Complication Requiring Surgical Repair or Blood Transfusion	2.3% (2/88)	1.1% (1/90)	1.2% [-4.0%, 6.9%]	
Mortality within 24 hours	2.3% (2/88)**	0.0% (0/90)	2.3% [-1.9%, 7.9%]	
In vivo Device Failure	0.0% (0/88)	0.0% (0/90)	0.0% [-4.1%, 4.2%]	

**STRYKER CONFIDENTIAL - THIS DOCUMENT CONTAINS CONFIDENTIAL AND PROPRIETARY INFORMATION THAT IS THE PROPERTY OF STRYKER CORPORATION. NEITHER THIS DOCUMENT NOR THE INFORMATION HEREIN MAY BE REPRODUCED, USED, OR DISCLOSED TO ANY THIRD PARTY WITHOUT THE PRIOR WRITTEN CONSENT OF STRYKER CORPORATION.**

## Trevo® Retriever Registry (China)

Endpoint	Trevo (N=88)	Merci (N=90)	Difference [95% CI] a	p-value
Other PR-SAE	0.0% (0/88)	0.0% (0/90)	0.0% [ -4.1%, 4.2%]	

\* Administration of IA t-PA was counted as a failure for post-device revascularization.

\*\* One death that occurred within 24 hours was related to the device, the other was attributed to the index stroke.

\*\*\*Patients who experienced more than one safety event are counted only once in the composite safety endpoint.

a: By normal approximation; b: non-inferiority hypothesis using Blackwelder's method with non-inferiority margin of 10%; c: One-sided Wald test of superiority; d: Fisher's exact test.

**Table 4. Secondary Endpoints in TREVO 2 (ITT population) **

Endpoint	Trevo (N=88)	Merci (N=90)	Difference [95% CI] a	p-value
Time to Revascularization (mins) b Mean ± SD (N) Median (min, max)	47.8±44.2 (79) 34.0 (6.0, 209.0)	47.3±38.8 (81)40.0 (4.0, 207.0)	0.5 [11.4%] c	< 0.0001 d 0.5326 e
90-Day Good Outcome (Modified Rankin Score 0-2)	40.0% (34/85)	21.8% (19/87)	18.2% [ 4.2%, 31.7%]	0.0130 f
90-Day Mortality	33.0% (29/88)	23.6% (21/89)	9.4% [ -4.2%, 22.7%]	0.1845 f
Asymptomatic ICH at 24 hours	40.9% (36/88)	53.3% (48/90)	-12.4% [-27.1%, 2.5%]	0.1017 f
Neurological Deterioration at 24 hours g	15.9% (14/88)	22.2% (20/90)	-6.3% [-18.4%, 5.5%]	0.3418 f

a: By normal approximation; b: Time to Revascularization was defined as the time from the start of the embolectomy procedure to achieving durable TICI 2a or better or to the end of the procedure if TICI 2a was not achieved. Subjects who had a baseline TICI score of 2a or did not have a study device used are excluded from this analysis (7 cases in Trevo arm, 8 cases in Merci arm); c: Per hypothesis testing setup, one-sided 95% upper confidence interval is used; d: One-sided Student's t-test of non-inferiority test with non-inferiority margin of 0.5 hours; e: One-sided Student's t-test of superiority test; f: Fisher's exact test; g: Defined as a four or more point increase in the NIHSS at 24 hours as compared to the baseline.

Overall the results of the TREVO and TREVO 2 trials demonstrate revascularization efficacy and safety of the Trevo Retriever.

**STRYKER CONFIDENTIAL - THIS DOCUMENT CONTAINS CONFIDENTIAL AND PROPRIETARY INFORMATION THAT IS THE PROPERTY OF STRYKER CORPORATION. NEITHER THIS DOCUMENT NOR THE INFORMATION HEREIN MAY BE REPRODUCED, USED, OR DISCLOSED TO ANY THIRD PARTY WITHOUT THE PRIOR WRITTEN CONSENT OF STRYKER CORPORATION.**

## Trevo® Retriever Registry (China)

### 3 Study Device Description

The Trevo Retriever is manufactured by Concentric Medical, a division of Stryker Neurovascular. The Trevo Retrievers consist of a self-expanding, laser cut, nitinol stent-like device permanently attached to a flexible, pusher wire. The retrievers have platinum markers at the distal end and platinum wires incorporated in the stent-like section to allow fluoroscopic visualization. (**Figure 1**). The packaged Retriever is pre-loaded into the Insertion Tool. The device has a hydrophilic coating to reduce friction during use and a shaft marker to indicate proximity of the Trevo tip relative to the microcatheter tip.

**Figure 1: Trevo ProVue Retriever**

Copyright © 2013 Stryker  
NV00004182.AA

Trevo® ProVue Retriever

During the procedure, the Trevo Retriever is delivered to the thrombus using a microcatheter. The microcatheter is then retracted to deploy the shaped section of the Retriever. The shaped section engages and traps the clot. The Retriever and microcatheter are pulled back to dislodge the thrombus. The Retriever, the thrombus, and the microcatheter are then removed from the body. Use of BGC (balloon guide catheter) and an intermediate catheter, such as DAC, are permitted but not required.

The Trevo Retriever has been designed and tested to perform multiple retrieval attempts in a single subject. Per the Instructions for Use (IFU), each Trevo Retriever may be used for up to three (3) retrieval attempts. After each deployment of the device it should be thoroughly cleaned and inspected before reloading. No more than six (6) retrieval attempts should be performed in the same vessel using any combination of retrieval devices. Refer to the IFU for detailed instructions on how to use the device. The Trevo Retriever should not be re-sterilized and reused.

There are no specific contraindications for the use of the Trevo Retriever apart from the inclusion and exclusion criteria of this Investigational Plan. Refer to the IFU for a listing of warnings and precautions.

## Trevo® Retriever Registry (China)

### 3.1 Device Labeling

A copy of the device Instructions for Use (IFU) is included in each device package. The Trevo labels and labeling contain the following information:

- Lot Number
- Expiration date

## 4 Registry Objective

### 4.1 Primary Objective

To assess real world performance of the CFDA cleared Trevo Retriever intended to restore blood flow in the neurovasculature by removing thrombus in patients experiencing ischemic stroke.

### 4.2 Secondary Objective

To identify optimal interventional techniques, including type of anesthesia, access, and method of clot retrieval, to result in successful outcomes.

To provide robust registry data that maybe used to support expanded indications in regulatory submissions and support reimbursement dossiers.

To gather significant amount of real-world safety data to allow further subset analyses.

## 5 Registry Endpoints

Clinical data will be evaluated in all subjects where the Trevo Retriever is used as the primary thrombectomy device to remove thrombus from the neurovasculature in the setting of acute ischemic stroke.

### 5.1 Primary Endpoint

Revascularization status at the end of the procedure using the modified TICI score.

### 5.2 Secondary Endpoints

- a. Day 90 mRS (good clinical outcomes defined as mRS of 0-2)
- b. Day 90 mortality
- c. Neurological deterioration at 24 hours, defined as a four or more point increase in the NIHSS score from the baseline score
- d. Rates of device and procedure related serious AEs

**STRYKER CONFIDENTIAL - THIS DOCUMENT CONTAINS CONFIDENTIAL AND PROPRIETARY INFORMATION THAT IS THE PROPERTY OF STRYKER CORPORATION. NEITHER THIS DOCUMENT NOR THE INFORMATION HEREIN MAY BE REPRODUCED, USED, OR DISCLOSED TO ANY THIRD PARTY WITHOUT THE PRIOR WRITTEN CONSENT OF STRYKER CORPORATION.**

## Trevo® Retriever Registry (China)

### 5.3 Other Key Parameters of Interest

The following time points will be collected on the electronic Case Report Forms (eCRFs): stroke symptom onset, admission to hospital/emergency department, diagnostic imaging, start of IV tPA, angio suite arrival, arterial puncture, clot integration, Trevo removal and end of procedure (defined as the time of the final cerebral angiogram).

Other data points will be collected include, but not limited to: time for activation of stroke team and time for stroke team response, type of anesthesia (GA vs. CS) and patient presentation (airway at risk, combative).

Data on the use of accessory products during Trevo thrombectomy such as the balloon guide catheter (BGC), intermediate catheters and time to deliver all accessory products will be collected.

De-identified images will be sent to a core lab for adjudication (e.g. CT/MRI scans and angiographies).

Information will be collected on factors influencing health economics in the treatment of stroke. . The data collected will consist of hospital charges for cases involving real world use of the Trevo Retriever. Collection of health economic information shall be disclosed to the subject in the Informed Consent Form (ICF).

## 6 Justification for the Registry Design

The data results from the TREVO and TREVO 2 trials demonstrate revascularization efficacy and safety of the Trevo Retriever. The Trevo Retriever Registry is a prospective, open-label, multi-center, international trial. The purpose of the Trevo Registry is to assess the performance of the Trevo retriever in real world practice to increase knowledge on the performance of the device, monitor safety outcomes, detect rare complications, and to obtain information for potential improvements for next generation devices.

### 6.1 Method of Enrollment

Clinical data points will be evaluated in all subjects who meet the inclusion/exclusion criteria and where Trevo Retriever is used as the initial mechanical thrombectomy device to remove thrombus from the neurovasculature in the setting of acute ischemic stroke. For purposes of this registry, enrollment occurs when the Trevo Retriever is deployed through the compatible Microcatheter into the neurovasculature as the first mechanical neuro-thrombectomy device used to remove the thrombus.

A Screening and Enrollment Log will be maintained by each site to document basic information such as date screened and reason for screen failures for subjects who fail to meet the study eligibility criteria. In order to avoid bias, if a center chooses to participate in the Trevo Registry, every effort should be made to include all Trevo cases performed over a given duration of time in the registry. No site will be allowed to enroll more than 30% of the entire maximum study population unless first approved by Stryker.

**STRYKER CONFIDENTIAL - THIS DOCUMENT CONTAINS CONFIDENTIAL AND PROPRIETARY INFORMATION THAT IS THE PROPERTY OF STRYKER CORPORATION. NEITHER THIS DOCUMENT NOR THE INFORMATION HEREIN MAY BE REPRODUCED, USED, OR DISCLOSED TO ANY THIRD PARTY WITHOUT THE PRIOR WRITTEN CONSENT OF STRYKER CORPORATION.**

# Trevo® Retriever Registry (China)

## 7 Study Population

### 7.1 Selection Criteria

#### 7.1.1 *Inclusion Criteria:*

1. Age  $\geq 18$
2. Subjects experiencing acute ischemic stroke due to a large vessel occlusion who are eligible and suitable for restoration of blood flow using any approved Trevo Retriever in the neurovasculature to remove thrombus
3. Trevo Retriever is planned to be the primary mechanical neuro-thrombectomy device to remove the thrombus
4. Subject or subject's legally authorized Representative (LAR) has signed the study Informed Consent Form
5. Subject willing to comply with the protocol follow-up requirements

#### 7.1.2 *Exclusion Criteria:*

1. mRS >2
2. Any known coagulopathy
3. Anticipated life expectancy less than 3 months
4. Known absolute contraindications to the use of required study medications or agents (e.g., heparin, aspirin, clopidogrel, radiographic contrast agents, etc.)
5. Preexisting neurological or psychiatric disease that would prevent complete the study required evaluations
6. The subject is participating in another mechanical neuro-thrombectomy device trial or any other clinical trial where the study procedure or treatment might confound the study end point.

### 7.2 Withdrawal and Replacement of Subjects

While study withdrawal is discouraged, subjects may withdraw from the study at any time, with or without reason and without prejudice to further treatment. Withdrawn subjects will not undergo any additional follow-up, nor will they be replaced. If a subject chooses to withdraw from the registry, the reason(s) for withdrawal will be recorded on the appropriate eCRF and in the medical record.

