## Trevo® Retriever Registry (China)

### 8.6.2 Day 90 ( $\pm 14$ )

At Day 90 ( $\pm 14$  days) the following study assessments should be performed:

- mRS score (see **Appendix F**) - If subject is unable to return to the clinic for the Day 90 visit, a telephone mRS assessment is preferable to no assessment
- SAEs related to the device or procedure
- For all subjects who expire prior to the Day 90 assessment, available information regarding the primary cause of death and date/time of death will be recorded, as well as whether the subject was made DNR or “comfort care only” prior to expiration.

Any death or SAE must be reported to Stryker Neurovascular within 24 hours of becoming aware of the event(s).

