### 9.2 Analysis Populations

The Intent-to-treat principle will be followed to define the analysis population. All of the subjects who signed the informed consent and in whom Trevo Retriever was deployed through the microcatheter are considered enrolled and will be included in the analyses.

Sub-group analyses for the Registry will be performed under guidance from the Study PIs, Steering Committee, and Sponsor.

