## 3. Analysis Population

The Intent-to-treat principle will be followed to define the analysis population. All subjects who signed the informed consent and in whom Trevo® Retriever was deployed through the microcatheter are considered enrolled and will be included in all the analyses.

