### 6.2. Final Report

Final report will be generated when all the 200 enrolled subjects complete their Day 90 visit or terminated before their Day 90.

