**Ver AA**

**Table 12: All SAEs**

	# of events	Percentages of subjects with events* (Total subjects=xxx)
All SAEs		
Details of all SAEs	xx	xx.x% (xx/xxx)
...	xx	
...	xx	xx.x% (xx/xxx)
...	xx	xx.x% (xx/xxx)
Study device and procedure related SAEs		
Total	xx	xx.x% (xx/xxx)
Details of study device and procedure related SAEs	xx	xx.x% (xx/xxx)
...	xx	xx.x% (xx/xxx)
...	xx	xx.x% (xx/xxx)
...	xx	xx.x% (xx/xxx)
Study device related SAEs only		
Total	xx	xx.x% (xx/xxx)
Details of study device related SAEs	xx	xx.x% (xx/xxx)
...	xx	xx.x% (xx/xxx)
...	xx	xx.x% (xx/xxx)
...	xx	xx.x% (xx/xxx)
Procedure but not study device related SAEs		
Total	xx	xx.x% (xx/xxx)
Details of procedure but not study device related SAEs	xx	xx.x% (xx/xxx)
...	xx	xx.x% (xx/xxx)
...	xx	xx.x% (xx/xxx)
...	xx	xx.x% (xx/xxx)
Study device or procedure related SAEs		
Total	xx	xx.x% (xx/xxx)
Details of study device or procedure related SAEs	xx	xx.x% (xx/xxx)
...	xx	xx.x% (xx/xxx)
...	xx	xx.x% (xx/xxx)
Not study device and not procedure related SAEs		
Total	xx	xx.x% (xx/xxx)
Details of not study device and not procedure related SAEs	xx	xx.x% (xx/xxx)
...	xx	xx.x% (xx/xxx)
...	xx	xx.x% (xx/xxx)

\*: Some subjects may experience multiple events

STRYKER CONFIDENTIAL - THIS DOCUMENT CONTAINS CONFIDENTIAL AND PROPRIETARY INFORMATION THAT IS THE PROPERTY OF STRYKER CORPORATION. NEITHER THIS DOCUMENT NOR THE INFORMATION HEREIN MAY BE REPRODUCED, USED, OR DISCLOSED TO ANY THIRD PARTY WITHOUT THE PRIOR WRITTEN CONSENT OF STRYKER CORPORATION

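### Protocol 7.2 ends follow-up for every withdrawn subject and defines no levels of withdrawal, although Protocol 14 and the SAP need outcomes on all enrolled subjects to Day 90

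*Protocol*

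**What the plan says.** Protocol 7.2 lets any subject leave whenever they wish: "subjects may withdraw from the study at any time, with or without reason and without prejudice to further treatment". The consequence is the same for all: "Withdrawn subjects will not undergo any additional follow-up, nor will they be replaced". The only item the section asks the site to record is why: "the reason(s) for withdrawal will be recorded on the appropriate eCRF and in the medical record". The section defines no levels of withdrawal. It provides for no closing check of vital status, function or safety.

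Protocol 9.2 sets the analysis set: "The Intent-to-treat principle will be followed to define the analysis population". SAP 3 says that consented subjects in whom the device was deployed "are considered enrolled and will be included in all the analyses". SAP 6.2 expects some early departures, since the final report waits until all 200 subjects "complete their Day 90 visit or terminated before their Day 90".

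Protocol 14 requires related SAEs and fatal SAEs to be reported through Day 90 and makes no exception for withdrawal. Protocol 8.6.2 accepts remote assessment for a subject who cannot attend the clinic: "a telephone mRS assessment is preferable to no assessment".

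**The concern.** Three of the four secondary endpoints need information up to Day 90: mRS, mortality, and device- and procedure-related SAEs (SAP 5.2.2). A site that follows 7.2 as written stops collecting this information at withdrawal, even if the subject or family would accept one telephone call or a look at the hospital record. In acute stroke, the decision to withdraw is plausibly linked to outcome, because a severely disabled subject, or a family acting for one, may be the more likely to leave. The rule can therefore turn recoverable data into informative missing data, while the subjects concerned stay in the analysis set. The registry aims to monitor safety, detect rare complications (Protocol 6) and support regulatory and reimbursement files (Protocol 4.2), so a safety rate that leans low matters.

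**Working it through.** **Step 1. The rules side by side, for a subject who withdraws before Day 90**

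- *Collection.* Protocol 7.2 ends follow-up. Protocol 14 wants related and fatal SAEs to Day 90. A site cannot satisfy both on their plain wording.
- *Analysis set.* SAP 3 retains the subject in all analyses.
- *Mortality.* SAP 5.2.2 classifies a subject who completed the Day 90 visit and a subject who missed it and is known to have died. It does not name a subject whose status is unknown. Its closing catch-all follows on from subjects who died; stretched to everyone else, it would count unknown status as death. The handling is undefined either way.
- *mRS.* A footnote to SAP Table 11 applies LOCF, so a discharge or Day 30 score can stand in for Day 90. The SAP does not say whether a pre-stroke score may be carried forward. SAP Table 7 lists pre-stroke scores of 0 to 2 only, so such a carry-forward would count as a good outcome.
- *SAEs.* The Table 12 shell is headed "Percentages of subjects with events* (Total subjects=xxx" and the SAP has no rule for incomplete follow-up. If withdrawn subjects stay in that denominator, an SAE after withdrawal cannot enter the numerator. The percentage can then only be too low, by 1/200 = 0.5 points per subject whose first related SAE is missed.

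**Step 2. Size**

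There is no plan figure to reproduce: SAP 4 gives N = 200 without a calculation, and neither document gives a withdrawal rate.

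Let m subjects withdraw with unknown Day 90 status and let x events be known among the other N − m, with x the whole number nearest to rate × (N − m). Then:

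- lowest possible rate = x/N (none of the m had the event)
- highest possible rate = (x + m)/N (all of them did)
- width = m/N, so 2/200 = 1 point for each 1% withdrawn

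Inputs: illustrative rates from Protocol Tables 1 and 4, namely mortality 20.0% (TREVO, 12/60) and 33.0% (TREVO 2 Trevo arm, 29/88), mRS 0–2 of 40.0% (34/85), and device-related SAEs 5.0% (3/60). The withdrawal rates are assumptions. The lowest, 3.4%, borrows the share without a Day 90 mRS in the TREVO 2 Trevo arm, (88 − 85)/88.

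| Outcome | 3.4% (m = 7) | 5% (m = 10) | 10% (m = 20) |
|---|---|---|---|
| Mortality near 20% | 39/200 to 46/200 = 19.5–23.0% | 38/200 to 48/200 = 19.0–24.0% | 36/200 to 56/200 = 18.0–28.0% |
| Mortality near 33% | 64/200 to 71/200 = 32.0–35.5% | 63/200 to 73/200 = 31.5–36.5% | 59/200 to 79/200 = 29.5–39.5% |
| mRS 0–2 near 40% (before LOCF) | 77/200 to 84/200 = 38.5–42.0% | 76/200 to 86/200 = 38.0–43.0% | 72/200 to 92/200 = 36.0–46.0% |
| Related SAE near 5% | 10/200 to 17/200 = 5.0–8.5% | 10/200 to 20/200 = 5.0–10.0% | 9/200 to 29/200 = 4.5–14.5% |

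The upper SAE bounds are extreme, since only events after withdrawal are lost.

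**Step 3. Bias or precision?**

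The Clopper-Pearson 95% interval for 20% mortality is 14.7–26.2% on 40/200 and 14.4–26.6% on 36/180. Losing 20 subjects hardly changes precision. What it adds is possible bias and an undefined denominator.

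**The case against.** The strongest reply is that 7.2 concerns a subject who leaves the registry, not one who misses visits. SAP Table 1 lists missed visits and early terminations separately, and a telephone mRS is allowed at Day 90. A reader might infer that 7.2 forces data loss even for a subject who simply stops attending. The documents do not say that, and such a subject can remain enrolled and be telephoned. What stands is that withdrawal is never defined, so a site that records a wish for no more visits as a withdrawal must then stop.

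One could also read the ban on follow-up as covering assessments of the subject only, leaving Protocol 14 in force for deaths and SAEs. That is a possible reading, but the text does not choose it, so the two sections still need reconciling.

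Three further inferences go too far:

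- *That Day 90 mRS is simply lost.* The SAP fills it by LOCF. The observed value is lost; the reported one is not.
- *That the SAP declares withdrawn subjects event-free.* It does not. This follows only if Table 12, a sample shell open to change under SAP 8, is used as drawn.
- *That TREVO 2 shows what a better withdrawal rule would recover.* Its Trevo arm reports mortality on 88 and mRS on 85, but the protocol does not say why three scores are missing or how that trial handled withdrawal.

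The loss may also be small. Across TREVO (60) and TREVO 2 (178), one of 238 subjects is outside the mortality denominators (Merci arm, 89 of 90), or 0.4%. That share would be about one subject in 200, or 0.5 points. Finally, the consent template (Protocol Appendix C) was not available to this review and may already govern data use after withdrawal.

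**Conclusion.** The point holds as a stated rule that works against the plan's own requirements. It rests on the wording of 7.2, the lack of an exception in Protocol 14, and the all-subjects rule in SAP 3. The consequence is a best/worst-case width of 1 point per 1% withdrawn: 5 points at an assumed 5%, against a full 95% interval of 26.2 − 14.7 = 11.5 points for mortality of 20%. If losses match the mortality denominators of the two earlier studies, it is about half a point. The bounds assume nothing about the missing subjects, and their ends require that none or all of them had the event.

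A reader might infer that the registry's main result is at risk. It is not: the primary endpoint is the mTICI score at the end of the procedure, and later withdrawal does not touch it. Nor do the documents show that withdrawal will be common. The change is worth making because it is cheap and the affected data are plausibly outcome-linked.

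**What to change.** Amend Protocol 7.2 to define two levels of withdrawal:

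1. The subject stops visits only. The site still obtains Day 90 vital status, a telephone mRS and related SAEs from the subject, the legally authorized representative or the record.
2. The subject withdraws consent to all further data collection. Nothing more is collected.

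Record the level on the withdrawal eCRF, align the consent form if it does not already cover this, and reconcile 7.2 with Protocol 14.

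In SAP 5.2.2 and Tables 11 and 12, report the number of subjects with incomplete follow-up to Day 90. Treat unknown vital status as unknown and give best/worst-case bounds. Do not count subjects with incomplete SAE follow-up as event-free without saying so.

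The cost is a short protocol amendment, an eCRF tick-box, possibly a line in the consent form, and a few calls or record checks. Protocol 17.2 requires amendments and consent changes to go to the ethics committee, which could involve up to 15 sites. The sample size stays at 200.
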